### *Flow cytometry*

To determine the impact of melatonin on NK cell markers, flow cytometry will be performed. Statistical analysis will be similar to that implemented in the cytokine analysis. Following confirmation of normality (KS-Test), a one-way anova will assess if any markers are significantly affected followed by a t-test corrected for multiple hypothesis testing (bonferroni) to identify which are significantly affected by melatonin treatment. If normality is not identified, a Kruskal–Wallis one-way anova will be performed to assess if any markers are significantly affected, followed by a Wilcoxon signed-rank test corrected for multiple hypothesis testing (bonferroni) to identify which are significantly affected by melatonin treatment.

### *NK cell cytotoxicity assay*

To characterize whether NK cells become activated following melatonin treatment, chromium release assays will be performed for both cohorts; those receiving melatonin (M) and those receiving placebo (P) treatment. Following fitting both cohorts to a model representative of each distribution, statistical analysis will be performed to assess if melatonin had a significant impact on NK cell impairment. This statistical analysis relies on the logarithmic error ratios (LER) for each treatment where  $LER = \log(SSR_M/SSR_P)$ , SSR is the sum of squared residuals and M/P are the models respective of each cohort. When the fits to M/P differ from one another, it is anticipated that the LER will be significantly different between both datasets. The subsequent probability associated with the null hypothesis that two fits perform equally well will be calculated by cross-validation. Briefly, 2 patients from each cohort are randomly selected to generate a training and validation datasets of equal size for each treatment. Following fitting the

data of each cohort using the training dataset, two LERs will be calculated using the validation dataset for each cohort. By repeating this process 1000 times, we will obtain a distribution of LER for each cohort. If LERs associated with the fits to M/P are normally distributed, a t-test will be performed to assess the likelihood that the killing assays are identical to one another.

In order to determine the reliability of the questionnaires evaluating the secondary outcomes, we will conduct an Analysis of Co-variance as well as determine Cronbach's alpha.

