## NSCLC Adjuvant melatonin RCT

- e) Melatonin will increase NK cell activity of people who are ingesting this at a dose of 20mg daily.
- f) Melatonin will create a decrease in both inflammatory and anti-inflammatory cytokines including: IL4, IL6, IL10, IL12, IL15, IFN- $\alpha$ , GM-CSF, TNF- $\alpha$ , IFN- $\alpha$ , TGF- $\beta$ 1, and VEGF in people who are ingesting melatonin at a dose of 20 mg daily.

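### The planned NK cytotoxicity test is an unsigned omnibus test with no effect estimate, although hypothesis (e) predicts an increase in killing

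*Combined protocol and SAP*

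**What the plan says.** Hypothesis (e) in Section 3 is directional: "Melatonin will increase NK cell activity of people who are ingesting this at a dose of 20mg daily". The NK cell cytotoxicity paragraph of Section 8 opens with the same question: "To characterize whether NK cells become activated following melatonin treatment".

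The analysis then proceeds as follows.

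- A model is fitted to each cohort, and the statistic is LER = log(SSR_M/SSR_P), where "SSR is the sum of squared residuals and M/P are the models respective of each cohort".
- A difference is expected to show in this way: "When the fits to M/P differ from one another, it is anticipated that the LER will be significantly different between both datasets".
- The null is that the two fits do equally well: "The subsequent probability associated with the null hypothesis that two fits perform equally well will be calculated by cross-validation".
- The resampling is described thus: "Briefly, 2 patients from each cohort are randomly selected to generate a training and validation datasets of equal size for each treatment". Then "two LERs will be calculated using the validation dataset for each cohort", and "By repeating this process 1000 times, we will obtain a distribution of LER for each cohort".
- If the LERs are normal, a t-test on them is read as evidence on whether the killing assays are the same in the two arms. This is a second null, wider than the first.

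The paragraph plans no difference in lysis, no confidence interval and no use of the baseline sample. Section 6.5 does collect one, four weeks after surgery and before treatment, with the endpoint sample at six months. Section 7.0 says that the 80-patient sub-study (40 per group) is powered for a 30% shift in NK functional activity. It gives no SD, alpha, sidedness or power.

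**The concern.** NK cell function is the first assay named in the second primary objective (Section 2.1), and the question is whether melatonin raises it. A ratio of squared residuals carries no sign and depends on between-patient spread as well as on the mean curve. A significant result could therefore reflect more killing, less killing or, depending on how the resampling is done, only a change in variability. Suppression would contradict hypothesis (e) and yet give the same test result as activation. Without a planned estimate and interval, the reader of the sub-study would have a p-value but no measure of how far killing moved, or which way.

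**Working it through.** **1. The plan's own figure.** The 30% shift with 40 per group cannot be reproduced, because the SD, alpha and power are missing. Assuming two-sided 0.05, the implied coefficient of variation is CV = 0.30 / [(1.96 + z_power) x sqrt(2/40)]:

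- 80% power: 0.30 / (2.80 x 0.2236) = 0.479
- 90% power: 0.30 / (3.24 x 0.2236) = 0.414

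The assumption used below, mean lysis amplitude 40 and SD 20 (CV 0.5), gives power of about 0.77 by the same formula. It is therefore close to what the plan would need.

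**2. What the LER contrast measures.** Take the literal text: two patients per cohort per draw, one for training and one for validation, with both models scored on each cohort's validation patient. Let sM and sP be the between-patient SDs and d the difference in mean killing, and ignore assay noise. In terms of expected squared error:

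- melatonin validation set: LER = log[2sM² / (sM² + sP² + d²)]
- placebo validation set: LER = log[(sM² + sP² + d²) / 2sP²]
- contrast (second minus first): log[(sM² + sP² + d²)² / (4 sM² sP²)]

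The difference d enters only as d², so its sign is lost. With d = 0 the contrast is still above zero whenever sM differs from sP.

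| Case (placebo mean 40, SD 20) | Contrast |
|---|---|
| d = +12 or -12 (30%), equal SDs | log(944²/800²) = 0.33 |
| d = 0, SD ratio 1.25 | 0.05 |
| d = 0, SD ratio 1.5 | 0.16 |
| d = 0, SD ratio 2 (or 0.5) | 0.45 |

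On this reading, halving the SD with no change in mean moves the statistic further than a true 30% shift.

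**3. Simulation, literal reading.** Inputs: 40 per arm, four effector:target ratios (Section 6.5), and 1000 draws. Mean 40, SD 20 and the assay noise are assumptions. The cut-off is recalibrated to 5% under identical arms, so the results do not depend on treating overlapping draws as independent.

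| Scenario | LER test rejects |
|---|---|
| +30% or -30% killing | about 50-55% (mean contrast 0.28 in both directions) |
| Equal means, SD x1.25 | about 5-9% |
| Equal means, SD x1.5 or x0.67 | 10-26% |
| Equal means, SD x0.5 | 33-58% |

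A Welch t-test on one summary per patient has about 75% power for the shift and rejects about 5% of the time when only the spread differs.

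A second model (a line in log effector:target ratio, CV 0.4 in the shift scenarios, noise SD 2) gives the same picture. Mean LERs on the melatonin and placebo sets are -0.24 and +0.23 for +30%, and -0.26 and +0.22 for -30%. Recalibrated spread-only rejection is 27% at a ratio of 1.5 and 68-71% at 2. Recalibrated power for the shift is 76-77%, against 92% for the per-patient test.

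**4. Half-split reading (20 training + 20 validation per arm).** With k training patients, the variance of the training mean is divided by k. At d = 0 the contrast becomes log[(sM² + sP²/k)(sP² + sM²/k) / (sM² sP² (1 + 1/k)²)]. For k = 20 and an SD ratio of 2 this is log[(4.05 x 1.20)/(4 x 1.1025)] = 0.10. A 30% shift with equal SDs gives 2 x log(564/420) = 0.59. Spread now matters little: simulated recalibrated rejection is about 4-14%, and power for the shift is 70-76% at mean 40 and SD 20. The sign is still lost: in the second model the mean LERs are -0.42 and +0.42 for +30%, and -0.41 and +0.41 for -30%.

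**5. Own-arm reading (each model scored only on its own arm).** The LER is then a ratio of within-arm residual variances. Recalibrated rejection for a true 30% shift is 6-8%, and for a twofold spread difference 97-99%. This reading fits the text poorly, since it yields one ratio per draw and not one LER per cohort.

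**The case against.** Several points on the other side have force.

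- **The second null.** The paragraph ends by asking whether the killing assays are the same in both arms. Under that null, arms with different spread are not the same, so rejecting on spread is not a false positive. This stands. What is left is that an omnibus null does not answer a question about the level and direction of killing.
- **Direction is not wholly out of reach.** A curve is fitted to each cohort and could be inspected after a significant result. The flow cytometry paragraph also plans arm comparisons of NK activation markers. Both are true. But inspection is not a planned test, and the markers do not replace the lysis result.
- **The size of the spread effect depends on assumptions.** The documents give no NK variance and no reason to expect a 1.5- to 2-fold difference in SD. At x1.25 the effect is close to nominal, and under a half-split it nearly disappears. This stands, and it shows that the spread problem comes largely from very small training sets.

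A reader might infer that the test is blind to a real change in killing. The text does not support that: on the literal and half-split readings it responds to a 30% shift, and only the ill-fitting own-arm reading misses it. A reader might also attribute every false positive here to the choice of null. Treating 1000 overlapping draws as independent is a separate defect. In the second model it gives 13% (literal) or 92% (20+20) rejection with identical arms before recalibration.

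**Conclusion.** The point holds in limited form. The loss of sign and the absence of an effect estimate do not depend on any assumed SD: they follow from the algebra whenever both models are scored on each arm, whether one or 20 patients are used for training. The reaction to spread and the lower power are conditional. They apply to the literal one-plus-one reading, and their size rests on the assumed mean of 40, SD of 20, assay noise and SD ratios. Under a 20+20 split, power is close to that of the per-patient test and the spread effect is small.

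The consequence is confined to one assay in a sub-study that Section 7.0 presents as an exploratory pilot. It would be wrong to infer that the recurrence and mortality analysis is affected. Severity is moderate to minor.

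**What to change.** Replace the LER procedure in the NK cytotoxicity paragraph of Section 8 with a patient-level comparison of percent specific lysis at six months:

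- Use either one summary per patient over the four effector:target ratios (mean or area under the curve) or a mixed model over the ratios with an arm effect.
- Adjust for the baseline value that Section 6.5 already collects, and allow unequal variances.
- Report the signed difference, melatonin minus placebo, with a 95% CI. Show curve shape and spread by arm descriptively.

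In the second model's simulated data, a Welch t-test on mean lysis rejected 3-6% of the time when the arms were equal or differed only in spread. Its power was about 92% for a 30% shift at CV 0.4, and every significant result in the shift scenarios had the correct sign. That check did not include baseline adjustment.

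The cost is one rewritten paragraph, with no new samples or assays. The rewrite also removes the resampling-independence problem. What is given up is a formal test of curve shape.

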## 2. Study Objectives

### 2.1 Primary Objectives

1. To determine the effectiveness of adjuvant melatonin as compared to placebo in the prevention of cancer recurrence and mortality two years after surgical resection of NSCLC.
2. To explore the effect of melatonin on promising biological markers within participants enrolled in the larger clinical trial. These markers include the most promising assays that address areas in which melatonin may act against cancer. The assays include NK cell function and cytokine levels. In addition to addressing the very important issue of mechanism of action, the additional 80 participants will further contribute to the power of the phase III trial.

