#### **i. Human NK cell cytotoxicity assay**

Human whole blood will be processed for Peripheral Blood Mononuclear cells (PBMCs) using Ficoll Paque (Stemcell). These will be used as Effector cells in an *ex vivo* NK cell cytotoxicity assay. The human NK cell sensitive tumor cell line – K562 (human leukemia) will be used as Target cells. K562 tumor cells will be harvested and labelled with 100 $\mu$ Ci of  $^{51}\text{Cr}$  (Perkin-Elmer) in the form of  $\text{Na}_2\text{CrO}_4$  for 1 hour. They will be added to the PMBCs in the 96-well plate at different effector to target cell ratios (25:1, 12:1, 6:1, 3:1). The mixture will be incubated for 4 hours prior to analysis of chromium release in the supernatant using a gamma counter (Perkin Elmer). To show NK cell specific lysis of tumor targets, NK cells will be depleted from PBMC population using CD56 microbeads (Miltenyi Biotech) in a control experiment where no killing of targets will be detected.

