## Phase II substudy analysis

### *Cytokine array*

To determine the impact of melatonin on patient cytokine levels, a cytokine array will be generated for each patient. Briefly, patients will be divided into two cohorts; those receiving melatonin and those receiving placebo treatment. Following data collection, cytokine expression measurements will be log transformed, and a KS-test will verify normality within each dataset. If confirmed, a one-way anova will assess if any cytokines are significantly affected, followed by a t-test corrected for multiple hypothesis testing (bonferroni) to identify which are significantly affected by melatonin treatment. If failed, a Kruskal–Wallis one-way anova will assess if any cytokines are significantly affected, followed by a Wilcoxon signed-rank test corrected for multiple hypothesis testing (bonferroni) to identify which are significantly affected by melatonin treatment.

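### The NK-cytotoxicity t-test treats 1000 resampled log error ratios per arm as independent data, although all come from about 40 patients per arm

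*Combined protocol and SAP*

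**What the plan says.** The substudy has 80 patients, 40 per group (Section 7.0). Each patient's lysis is measured at four effector-to-target ratios, 25, 12, 6 and 3 to 1, before treatment and at six months (Section 6.5).

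Section 8, NK cell cytotoxicity assay, sets out these steps:

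- The draw: "2 patients from each cohort are randomly selected to generate a training and validation datasets of equal size for each treatment".
- The statistic: LER = log(SSR_M/SSR_P), the log ratio of the squared residuals from the melatonin and placebo fits. After fitting on the training data, "two LERs will be calculated using the validation dataset for each cohort".
- The repetition: "By repeating this process 1000 times, we will obtain a distribution of LER for each cohort".
- The test: "If LERs associated with the fits to M/P are normally distributed, a t-test will be performed".

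The section does not return to the patient as the unit, adjust the variance for resampling or permute treatment labels. It names no normality check and no alternative if normality fails. The Cytokine array paragraph supplies both: "a KS-test will verify normality within each dataset", and on failure a rank analysis "followed by a Wilcoxon signed-rank test corrected for multiple hypothesis testing (bonferroni) to identify which are significantly affected by melatonin treatment". (Whether that test suits two independent arms is a separate matter.)

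On the importance of the assay, Section 2.1 says under Primary Objective 2: "The assays include NK cell function and cytokine levels". Hypothesis (e) in Section 3 predicts higher NK activity on melatonin.

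**The concern.** A t-test takes its standard error from the spread of independent observations and their number. Here the observations are computer draws from a fixed set of patients. More draws add no information about melatonin, yet they shrink the standard error.

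Cross-validation is a sound way to estimate prediction error. The fault is the next step, which tests the resampled values as if each were new data. A nominally significant NK result could then be chance imbalance between two groups of 40, made to look precise by repetition. Because this is the plan's only stated test of the cytotoxicity assay, a false mechanistic claim could follow.

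**Working it through.** **1. The plan's own figure.** Section 7.0 says the substudy is powered for a 30% shift in NK activity with 40 per group. It gives no SD, alpha or power. For a patient-level two-group comparison at two-sided 5% (assumed), power ≈ Φ(0.30 × √(40/2) / CV − 1.96), where CV is the between-patient SD divided by the mean. At CV 0.479 this is Φ(2.80 − 1.96) = 80%. At CV 0.30, 0.40, 0.60 and 0.80 it is 99%, 92%, 61% and 39%. The claim can be neither confirmed nor refuted.

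**2. Counting units.** With 1000 LERs per arm, a two-sample t-test has 2 × 1000 − 2 = 1998 degrees of freedom. Forty patients per arm give 2 × 40 − 2 = 78. For the same spread, a standard error based on 1000 values is smaller than one based on 40 by a factor √(1000/40) = 5.

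**3. Mechanism.** Take the 80 patients as fixed. The repeats are then draws from a fixed population of possible LERs. The mean LERs of the two arms in that population differ by some amount D. With no treatment effect D averages zero over trials, but in any one trial it is not zero, and its size depends on the patients alone. With B repeats and LER standard deviation s, the t statistic centres on D / (s√(2/B)) = (D/s) × √(B/2). It grows with √B.

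**4. Size with no treatment effect.** Assumptions, since the documents give none: a straight line in log2 of the ratio at the four stated ratios; 40 per arm; two-sided 5%; between-patient/residual SDs of 5/4, 10/5 and 12/4 points of lysis, each with slope SD 0 or 3; 4000 simulated trials per setting. The literal reading is one training and one validation patient per arm.

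| Reading | 100 repeats | 1000 repeats | 10,000 repeats |
|---|---|---|---|
| 1+1 split, two-sample t | 3.5–4.2% | 11–14% | 49–52% |
| 1+1 split, paired t | – | 16–18% | – |
| 2+2 split, two-sample t | – | 21–23% | – |
| 20+20 split, two-sample t | – | 93–95% | – |

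An ordinary patient-level t-test on the same data gives 4.6–5.8%. The 2+2 and 20+20 rows (800 trials per SD pair) are not conditioned on normality. The LER is scale-free, so with a random intercept only the SD ratio matters; ratios from 0.5 to 5 give 10.9–13.1% at 1000 repeats. Other SD pairs (8/3, 12/3, 8/8; 600 trials each) give 11–15% for the 1+1 split. The paired version is a possible reading because both LERs of a repeat share the same two fits.

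**5. One fixed null data set** (patient-level p = 0.11, 40 per arm), changing only the number of repeats:

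| Repeats | p, 1+1 split | p, 2+2 split |
|---|---|---|
| 40 | 0.88 | 0.63 |
| 100 | 0.91 | 0.22 |
| 1000 | 0.14 | 0.0099 |
| 10,000 | 3 × 10⁻⁶ | 3 × 10⁻²⁵ |
| 100,000 | 7 × 10⁻⁶⁹ | 2 × 10⁻¹⁸² |

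**6. The normality condition.** Both LER sets checked at 5%, 1+1 split, 1000 repeats:

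| Check | Trials passing | Pass and reject, of all trials |
|---|---|---|
| Plain KS | 95–99% | 11–13% |
| Lilliefors | 41–74% | 5–9% |
| Shapiro-Wilk | 19–63% | 2–8% |

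Given a pass, the error is 11–14% under all three. A strict check lowers the overall rate only because the test is then often not run, and the plan puts nothing in its place.

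**The case against.** - **Patients do matter.** At 1000 repeats, false rejection is about 64% with 10 patients per arm, 28–34% with 20, 11–14% with 40 and 6% with 80. This stands: patient number governs how far the arms differ by chance. But the test's standard error does not use that number, so the level is right only if repeats and patients happen to balance. At 100 repeats it is even slightly conservative.
- **The repeat count is fixed at 1000 in advance.** True. The 100 and 10,000 figures are hypothetical and show the mechanism; they are not what the plan will do. At the planned 1000 the error is still more than twice nominal whenever the test is run.
- **The size is not determined by the documents.** Also true. Split, curve model, SDs and t-test type are open, and the readings run from 11–14% to 93–95%. The direction is firm, since inflation at 1000 repeats appeared under every reading tried. The exact figure is not.
- **It is exploratory.** Section 7.0 calls this an exploratory pilot, no alpha or decision hangs on it, NK markers are also analysed by flow cytometry, and the chi-square test of the main outcome is untouched. This limits the consequence. It does not make the p-value valid, and the plan uses it to judge whether melatonin had a significant effect.
- **The missing fallback is a separate gap.** Agreed. It is not evidence of the resampling error, but it lies in the same paragraph and the same rewrite closes it.

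**Conclusion.** The concern holds. As written, the p-value takes its precision from resamples rather than from the roughly 40 patients per arm, and nothing elsewhere in the plan restores the patient as the unit. On the literal reading and the stated assumptions, a nominal 5% test is falsely significant in about 11–14% of null trials when it is run, and in more under the paired or larger-split readings. The reach is confined to one substudy assay. It should be fixed, because the assay serves a named objective and the repair needs no new data.

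**What to change.** Replace the t-test on resamples with one pre-specified test that has the patient as the unit (n = 80), and state alpha. Choose one option before unblinding.

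- **Option A, keep the LER.** Average the between-arm LER difference over draws and take the p-value by permuting treatment labels across the 80 patients. No normality condition is needed. Simulated null error with 399 permutations: 5.0–5.9%. Permuting within stage stratum would match the randomization in Section 6.4. Ignoring stage costs little: with an assumed 10-point stage effect, free permutation gave 4.2%.
- **Option B, one value per patient.** Average the four lysis values at each visit and compare six-month means by ANCOVA with the baseline value, already collected, as covariate. Simulated null error: 4.4–5.5%.

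The cost is one paragraph; assays, visits and data are unchanged. The apparent precision falls, since 1000 v 1000 becomes 40 v 40. Power for the 30% shift, taken as a uniform rise of 0.30 × 17.1 = 5.1 points on an assumed mean lysis of 17.1:

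| SDs | Planned test, inflated level | Planned test held to 5% (absolute t above 2.6) | A | B, baseline correlation 0 | B, correlation 0.5 |
|---|---|---|---|---|---|
| 5/4 | 95.6% | 93% | 96.5% | 99% | 99.7% |
| 10/5 | 50.4% | 40% | 49.5% | 60% | 71% |
| 12/4 | 36.4% | 26% | 33.3% | 47% | 56% |

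Option A can lose a little nominal power but gains once the planned test is held to its stated level. Option B's gain depends partly on the baseline correlation. If melatonin instead multiplies the whole curve by 1.3 and baseline is uninformative, B falls below the planned test's nominal power in the two noisier settings (60% v 71%, 47% v 59%). B also asks about mean lysis, so it could miss a pure change in curve shape. If curve shape is the question, A is the closer replacement.
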